# **Abbreviations**

ADE Adverse Device Effect

AE Adverse Event

ASADE Anticipated Serious Adverse Device Effect

BoP Bleeding on Probing

ECRF Electronic Case Report Form

DD Device Deficiency

EC Ethics Committee

EDC Electronic Data Capturing

FMPS Full Mouth Plaque Score

GCF Gingival Crevicular Fluid

GCP Good Clinical Practice

IfU Instructions for Use

ISO International Organization for Standardization

ISQ Implant Stability Quotient

ITI International Team for Implantology

MBL Marginal Bone Loss

OHRQoL Oral Health Related Quality of Life

OHIP Oral Health Impact Profile

PPD Probing Pocket Depth

RFA resonance frequency analysis

SADE Serious Adverse Device Effect

SAE Serious Adverse Event

SLA® Sandblasted, large-grit, acid-etched (surface)

SLActive® Chemically modified SLA® (surface)

UFS Ultra-fine structure

USADE Unanticipated Serious Adverse Device Effect

# Synopsis

- Oyliopsis					
Study Title	A randomized controlled study to assess intra-patient clinical performance of dental implants with a SLActive® vs. SLA® surface				
Study Protocol Number	CR 2017-05				
Study Registration	clinicaltrials.gov (NCT03737357)				
Objectives	
 
to confirm safety and clinical performance of SLActive® implants
 
to evaluate the osseointegration and anti-inflammatory potential of the SLActive® surface compared to SLA®.
 
				
Hypotheses	
 
Co-primary study hypotheses:         
 
SLActive® implants are safe
 
12 months after loading, the marginal bone loss around the SLActive® implants will not be appreciably greater than around the SLA® implants.
 
 
 
Secondary study hypotheses:         
 
SLActive® implants show superior osseointegration compared to SLA® as tested by biomarker analysis
 
SLActive® implants show superior anti-inflammation compared to SLA® as tested by biomarker analysis
 
 
 
				
Design	Prospective, single-blinded, randomized, paired sample, multi-center clinical study				
Study Population	Male or female subjects over 18 years of age and in need of two or more dental implants (canine to molars) placed in two different quadrants.				
Patient Inclusion Criteria	
 
The following criteria must be met for inclusion in the study:
 
Males and females, at least 18 years old
 
Partially edentulous patients in need of two or more dental implants (canine to molars) placed in two different quadrants in healed sites (3 months post extraction)
 
Subject must have voluntarily signed the informed consent, is willing and able to attend scheduled follow-up visits, and agrees that the encoded data will be collected and analyzed
 
				
Patient Exclusion Criteria	
 
Any contraindications for oral surgical procedures
 
Dental implant placement contraindicated according to Instructions for Use (IFU)
 
Subjects with inadequate oral hygiene (FMPS ≥ 20%)
 
Subjects who are currently heavy smokers (defined >10 cigarettes per day or >1 cigar per day) or who use chewing tobacco.
 
Subjects with drug or alcohol abuse
 
Patients requiring soft tissue and bone grafting procedures
 
Patients having had soft tissue grafting procedures within the last 3 months and bone grafting procedures within the last 6 months in the region where a study implant is planned
 
Keratinized soft tissue height of less than 2 mm where a study implant is planned
 
Inadequate bone volume
 
Severe bruxism or clenching habits
 
Women who are pregnant or planning to become pregnant at any point during the study duration.
 
patients who have systemic factors that could interfere with the healing process of either bone or soft tissue or the osseointegration process (e.g. bone metabolism disturbances,
 
				

	uncontrolled diabetes mellitus, anticoagulation drugs/ hemorrhagic diatheses)  • patients with local factors that could interfere with the healing process, such as untreated periodontal diseases, acute infection of implant site, temporomandibular joint disorders, treatable pathologic diseases of the jaw and changes in the oral mucosa)  • Conditions or circumstances, in the opinion of the investigator, which would prevent completion of study participation or interfere with analysis of study results, such as history of non- compliance, or unreliability.  One study test (SLActive® surface) and one study control (SLA® surface)				
Study Treatment	implant (Bone Level Tapered, Roxolid®) will be placed in two different quadrants of partially edentulous patients. The implants will be placed at premolars, molars and canine positions in the mandible and maxilla (healed extraction sites). Implants will be restored with a single crown or splinted restorations 10 weeks after implant placement.				
	Visit #	Visit	Schedule		
	Visit 1	Screening	Up to 10 weeks before implant placement		
	Visit 2	Implant placement and sampling (baseline)	Day 0		
	Visit 3 Sampling, suture removal		1 week (+/-1 days)		
Treatment Plan	Visit 4	Sampling	2 weeks (+/-2 days)		
	Visit 5	Sampling	4 weeks (+/-3 days)		
	Visit 6 Sampling, final impression 8 weeks (+/-		8 weeks (+/-5 days)		
	Visit 7 Implant loading		10 weeks (+/- 10 days)		
	Visit 8 6-month FU		6 months (+/-2 week) after loading		
	Visit 9 12-month FU		12 months (+/-3 weeks) after loading		
Test Device	Bone Level Tapered (BLT) Roxolid® implants with a SLActive® surface (8, 10, 12 or 14 mm length and 3.3 or 4.1 mm diameter).				
Control Device		_T) Roxolid® implants wi and 3.3 or 4.1mm diame			
Registration Status	All products are CE marked and used within their intended purpose				
Analysis	The final analysis will be conducted after all patients completed the 12-month visit. Optional interim analysis will be performed after all patients completed the completion the 8 weeks follow-up visit.				
	- Bone level change at 12 months after implant loading.				
Primary Endpoints	Occurrence of adverse device effects and device deficiencies that could have led to a serious adverse device effect				
Secondary Endpoints	
 
Bone level change (between implant placement and loading and between loading and 12 months after implant loading).
 
Changes of biomarkers in GCF in regards to:         
 
Inflammation (between implant placement and 30 days):
 
 
 
				

	Anti-inflammatory biomarkers analysis (concentrations of IL-10				
	and IL-4)				
	Inflammatory biomarkers (concentrations of IL-6, IL-1 β TNF-α, IL-2)				
	
 
Osseointegration (between day 7 and 8 weeks): concentrations of VEGF Osteocalcin (OCN), osteopontin (OPN)
 
				
	- Bacterial load analysis (between implant placement and 30 days)				
	- Implant stability (with ISQ) (between implant placement and 8 weeks)				
	
 
Soft tissue/ wound healing (Landry index) (between suture removal and 14 days)
 
				
	- Clinical measurements				
	Keratinized tissue height at implant placement and after 12 months. Probing pocket depth (PPD) and Bleeding on Probing (BoP) after 12 months				
	FMPS (at screening and after 12 months)				
	- Implant survival (up to 12 months)				
	
 
Prosthetic success (prosthetic survival and prosthetic complications)
 
(up to 12 months)
 
				
	
 
Patient satisfaction (OHRQoL, OHIP-14 questionnaire) (at screening, loading and after 12 months)
 
				
Safety	The patients will be monitored for AEs and device deficiencies by the Investigators.				
Participating Countries	Spain				
Number of participating centers	2 (one university hospital in Madrid and one university hospital in Santiago de Compostela)				
Number of Patients planned to be enrolled	60				
Study Duration	Approximately 26 months in total. Study started in October 2019, end of the study planned in November 2021				
Follow-up period	12 months from loading (loading after 10 weeks)				
Sponsor	Institut Straumann AG				
Investigators	[name] [name], Universidad Complutense (Complutense University), Facultad de Odontologia, [name], [name], Spain (Coordinating Investigator)				
	[name] [name], Universidad de Santiago de Compostela, Facultad de Medicina y odontología, Departamento de Cirugía y Especialidades médico-quirúrgicas (Odontología), Unidad de Periodoncia, [name], [name], Spain				
Compliance	This study and any amendments will be performed according to International Organization for Standardization (ISO) 14155:2011 as far as applicable for post-market studies, local legal and regulatory requirements, and conform to the Declaration of Helsinki (last revision Fortaleza 2013).				

# 1 Background and Study Rationale

Restoring missing teeth with dental implants is becoming a mainstream treatment option and patients expect successful and predictable treatment results. The clinical success of oral implants depends on the interaction with surrounding bone ultimately resulting in osseointegration. An important role thereby plays the implant surface (1) (2). SLActive® (Chemically modified Sandblasted, large-grit, acid-etched) is a hydrophilic, chemically active implant surface with ultra-fine structures. The surface has been investigated in various preclinical and clinical studies and the results showed high predictability and accelerated osseointegration (3) (4) (5) (6) (7) (8) (9) (10) (11) (12) compared to hydrophobic surfaces.

Straumann has optimized the production process of Straumann® SLActive® implants to better control the SLActive® surface properties. Under normal storage conditions – storage in an aqueous saline solution at a room temperature (for details see the surface research document PDD-00017370 (13)), SLActive® implants spontaneously develop ultra-fine structures (UFS) within 2 to 6 months. Now, a postproduction-holding step at 55°C has been introduced to ensure that the SLActive® surface achieves a fully mature surface when placed on the market.

The purpose of this post-market study is to re-confirm safety and performance of SLActive® implants produced under the optimized production process by monitoring crestal bone levels and adverse device effects and device deficiencies that could have led to a serious adverse device effect over time. As the highest incident of bone loss around implants is within the first 12 months according to literature (14), a follow-up of 12 months was chosen. SLA® (w/o ultrafine structure) will be used as a control device in this study. It was launched in 1994 and is considered to be one of the best-documented rough surfaces in implantology (15) (16). As mentioned earlier, SLActive® was associated with accelerated osseointegration properties (3) (4) (5) (6) (7) (8) (9) (10) (11). The osseointegration potential of SLActive® will be confirmed using a common method to assess osseointegration, resonance frequency analysis (RFA) (17) (with Osstell ISQ scale), and further investigated with regards to the underlying mechanisms by testing different osseointegration markers. In addition, the inflammatory and anti-inflammatory potential of the two surfaces will be assessed as inflammation plays an important role in osseointegration, particularly during the acute inflammatory response triggered in the early periods after surgery (18) (19) (20) (21).

Besides in-vitro studies (22) (23) (24), there were a few clinical studies performed looking at the expression of osseointegration markers on the SLActive® and SLA® surface (25) (26). Whereas Donos et al, observed an up-regulation of osteogenesis- and angiogenesis-associated gene expression on the SLActive® surface by day 7, Dolanmaz didn't find a difference between the two surfaces. Further clinical studies investigating osseointegration markers expression are

necessary to confirm the osseointegration potential of SLActive® shown in studies using RFA (11) (27) (28) analysis .

Inflammatory and anti-inflammatory markers are often assessed when comparing periodontitis patients with healthy patients (29) (30) (31). SLActive® has shown anti-inflammatory potential compared to the SLA® surface in in-vitro and pre-clinical studies (32) (22) (33) (34) but clinical data are still missing. Furthermore, no clinical studies investigating osseointegration markers and their correlation with inflammatory markers (cytokines) are known so far.

# 2 Objectives

#### 2.1 Study Hypothesis

Based on previous obtained data the expectations are as follows:

Co-primary study hypotheses:

- 1) SLActive® implants are safe
- 2) 12 months after loading, the marginal bone loss around the SLActive® implants will not be appreciably greater than around the SLA® implants.

Secondary study hypotheses:

- SLActive® implants show superior osseointegration compared to SLA® as tested by biomarker analysis
- 4) SLActive® implants show superior anti-inflammation compared to SLA® as tested by biomarker analysis

# 2.2 Primary Objective

The primary objective of this post-market study is to re-confirm safety and performance of SLActive® implants by means of bone level change 12 months after implant loading and monitoring of adverse device effects and device deficiencies that could have led to a serious adverse device effect.

# 2.3 Secondary Objectives

The secondary objectives of this study are to evaluate the osseointegration and anti-inflammatory potential of SLActive® implants compared to the SLA® surface. Implant stability (with ISQ) and osseointegration, inflammatory- and anti-inflammatory biomarker expression will be assessed during the early healing phase.

# 3 Study Design

#### 3.1 Type and Design of the Study

This is a prospective single-blinded, randomized, paired sample, multi-center clinical study.

## 3.2 Indications and Contra-Indications

Straumann® Bone Level Tapered (BLT), Roxolid® SLActive® and SLA® implants are suitable for the treatment of oral endosteal implantation in the upper and lower jaw and for the functional and esthetic oral rehabilitation of edentulous and partially dentate patients.

Placing small-diameter implants (diameter 3.3 mm) in the molar region is not recommended.

#### Contra-Indications are:

- Non-completed jawbone growth, drug or alcohol abuse, allergies or hypersensitivity to chemical ingredients of materials used: titanium-zirconium alloy, all conditions which would be normally contraindicated for oral surgery.
- Inadequate bone volume and/or quality, local root remnants, serious internal medical problems, uncontrolled bleeding disorders, inadequate wound healing capacity, not completed maxillary and mandibular growth, poor general state of health, uncooperative, unmotivated patient, drug or alcohol abuse, psychoses, prolonged therapy-resistant functional disorders, xerostomia, weakened immune system, illnesses requiring periodic use of steroids, uncontrollable endocrine disorders. Allergies or hypersensitivity to chemical ingredients of materials used: titanium-zirconium alloy.

The complete details of the Instructions for Use (IfU) for the Straumann® Bone Level Tapered Roxolid® SLActive® and SLA® implants can be found in the Annex 1 and Annex 2.

# 3.3 Study Treatment

Patients will receive Straumann® Bone Level Tapered (BLT), Roxolid® implants with a SLActive® surface (test device) and a SLA® surface (control device) within the intended use (see IfU in Annex 1, Annex 2). Based on randomization (0), two different quadrants will be assigned for either control or test implant placement (study test and study control quadrant). Indications sites are premolars, molars and canines in mandible and maxilla and extraction need to have been performed more than 3 months ago (healed extraction sites). Implants will be 8, 10, 12 or 14 mm of length and with a diameter of 3.3 or 4.1 mm. Particular care should be used when placing small-diameter implants (diameter 3.3 mm) in the molar region.

Per patient, one control and one test implant will be appointed as study control and study test implant ("study implants"). An implant (test or control device) qualifies as study implant if the implant is assessed as primary stable (as defined in Section 7.2.3), the abutment torque is at least 15 Ncm at surgery and the implant site fulfills the eligibility criteria (canine to molar, extraction/ tooth loss more than 3 months ago, soft tissue grafting procedures more than 3 months and bone grafting procedures more than 6 months ago). If there are several control or test implants placed in a study quadrant which qualify as study implant, the most mesial implant satisfying all the criteria, will be appointed as study implant.

Screw retained abutments (SRA) of 2.5mm height will be placed at the same time as the implants and covered with a healing/ protective cap. The implants will be restored with a single crown or splinted restorations 10 weeks after implant placement (implant loading).

Further details can be found under 7.2 (treatment procedures)

# 3.4 Endpoints

#### 3.4.1 Primary Endpoint

The following parameter will be measured as primary endpoint:

- Bone level change 12 months after implant loading.
- Occurrence of adverse device effects and device deficiencies that could have led to a serious adverse device effect

# 3.4.2 Secondary Endpoints

The secondary objectives assessed are:

- Bone level change (between implant placement and loading and between loading and 12 months after implant loading)
- Changes of biomarkers in GCF in regards to:
  - Inflammation (between implant placement and 30 days):
     Anti-inflammatory biomarkers analysis (concentrations of IL-10 and IL-4)
     Inflammatory biomarkers (concentrations of IL-6, IL-1β, TNF-α, IL-2)
  - Osseointegration (between day 7 and 8 weeks):
     Concentrations of VEGF, Osteocalcin (OCN), Osteopontin (OPN)
- Bacterial load analysis (between implant placement and 30 days)
- Implant stability (with ISQ) (between implant placement and 8 weeks)
- Soft tissue/ wound healing (Landry index) (between suture removal and 14 days)
- Clinical measurements
  - o Keratinized tissue height at implant placement and after 12 months
  - Probing pocket depths (PPD) and Bleeding on Probing (BoP) after 12 months. It is not the idea to evaluate a change but rather the occurrence after 12 month and possible differences between groups as these parameters are an indicator to determine the incidence of peri-implant diseases.
  - o FMPS (at screening and after 12 months)
- Implant survival
- Prosthetic success (prosthetic survival and mechanical complications acc. to ITI Treatment Guide Volume 8 (37))

Patient satisfaction (OHRQoL, OHIP-14 questionnaire) (at screening, loading and after 12 months)

# **3.4.3 Safety**

Safety will be assessed as described in Section 8

# 3.5 Study Sample Size

It is planned to enroll 60 patients into the study at 2 study centers. It is expected that both centers enroll approximately 30 patients (20 subjects at a minimum and 40 at a maximum). Details of sample size calculation are given in section 9.4.

# 3.6 Study Duration

The first patient was enrolled in the study in October 2019 and it is expected that recruitment will be completed after 12 months. Each patient will be followed for 12 months and implant loading and data will be collected during this time period. Hence, the end of the study is planned to be November 2021.

## 3.7 Study Population

The study population will consist of male or female patients, 18 years of age or older, who are in need of at least two dental implants (canine to molars, healed sites) placed in two different quadrants and meet all of the inclusion (Section 3.7.1) but none of the exclusion criteria (Section 3.7.2).

Patients must provide their written informed consent for study participation prior to any study related procedures (Section 7.1.1). Patients having signed the Informed Consent Form need to be entered in the Screening and Enrollment Log and are considered "enrolled" in the study. Patients who do not meet eligible criteria are considered "screening failures" (Section 11.3.6). Patients will be withdrawn from the study for the cases defined under 3.7.3.

#### 3.7.1 Inclusion Criteria

The following criteria must be met for inclusion in the study:

- Males and females, at least 18 years old
- Partially edentulous patients in need of at least two dental implants (canine to molars)
   placed in two different quadrants in healed sites (3 months post extraction)
- Subject must have voluntarily signed the informed consent, are willing and able to attend scheduled follow-up visits, and agree that the encoded data will be collected and analyzed

#### 3.7.2 Exclusion Criteria

The following exclusion criteria will lead to exclusion from the study:

- Any contraindications for oral surgical procedures
- Dental implant placement contraindicated according to Instructions for Use (IFU)
- Subjects with inadequate oral hygiene (FMPS ≥ 20%)
- Subjects who are currently heavy smokers (defined >10 cigarettes per day or >1 cigar per day) or who use chewing tobacco
- Subjects with drug or alcohol abuse
- Patients requiring soft tissue and bone grafting procedures
- Patients having had soft tissue grafting procedures within the last 3 months and bone grafting procedures within the last 6 months in the region where a study implant is planned
- Keratinized soft tissue height of less than 2 mm where a study implant is planned
- Inadequate bone volume
- Severe bruxism or clenching habits
- Woman who are pregnant or planning to become pregnant at any point during the study duration.
- patients who have systemic factors that could interfere with the healing process of either bone or soft tissue or the osseointegration process (e.g. bone metabolism disturbances, uncontrolled diabetes mellitus, anticoagulation drugs/ hemorrhagic diatheses)
- patients with local factors that could interfere with the healing process, such as untreated periodontal diseases, acute infection of implant site, temporomandibular joint disorders, treatable pathologic diseases of the jaw and changes in the oral mucosa)
- Conditions or circumstances, in the opinion of the investigator, which would prevent completion of study participation or interfere with analysis of study results, such as history of non-compliance, or unreliability.

#### 3.7.3 Withdrawal criteria

The Investigator must withdraw any patient from the study in the case of:

- No control and test implants received/ placed at visit 2
- No control and test implant (one of each) available that qualify as study implants (implant is
  assessed as primary stable (as defined in Section 7.2.3) at surgery, the abutment torque is
  at least 15 Ncm at surgery and the implant site fulfills the eligibility criteria, see Section 3.3
  for further details), in 2 different quadrants.

The Investigator may withdraw any patient from the study in the case of:

- Non-compliance with the protocol
- · Failure to attend the follow-up visits
- SAE or AE, which in the opinion of the Investigator prevents the patient's further participation in the study.
- Subject requires surgical treatment during the course of the study in the region of the mouth being evaluated in the study

Any patient may withdraw from the study any time without prejudice and will be offered an alternative treatment related to their dental condition. Patients will be advised of the need for the prescribed follow-up visits for their ongoing care, well-being, and collection of any safety data.

The patient withdrawal will be documented on a Study Termination eCRF page and must include the reason for the patient withdrawal. Withdrawn patients will be replaced in case the recruitment is still ongoing. As soon as recruitment is completed withdrawn patients will not be replaced.

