## 7.3.8 Implant Survival

Implant survival will be defined as follows:

A surviving implant is defined as an implant in place at the time of the follow-up. Any implant loss shall be assessed as an early loss (implant fails before being osseointegrated) or late loss (after being osseointegrated).

The basis for implant survival analysis are the study control and study test implants within the ITT population. Implant losses of the other implants will be recorded as AE's.

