#### 7.3.12 Adverse Events

Adverse Events (AE) collection for each patient will start at Screening Visit and ends after a patient withdraws from the study or completes the final study visit. At each visit, the Investigator should determine if any adverse events occurred since the last study visit by inquiring with the patient and reviewing any dental and medical records. These AEs, along with any AEs from the current study visit, should be documented on the appropriate eCRF form (specifying the region/implant position(s) concerned or related to (for a procedure) and using the AE terms from Table 5 if applicable) and reported as described in Section 8 of the protocol. In addition the Investigator should evaluate the status of any ongoing AEs throughout the study as specified in Section 0.

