#### 7.3.13 Device Deficiencies

Device Deficiencies will be recorded for all Straumann products used for the treatment (including prosthetic components and instruments). Device Deficiency collection for each patient will start at Visit 2 (surgery visit) and ends after the last study required treatment.

If a DD leads to an AE (e.g., bleeding, pain, swelling, infection, peri-implantitis) or SAE (e.g., nerve encroachment, sinus perforation, etc.) the respective adverse event eCRF form should as well be completed and the process for adverse events followed (as described in Section 7.3.12 above).

DDs should be documented on the appropriate eCRF form (specifying the article number and Lot.nr of the device concerned and the implant position if applicable) and reported as described in Section 8 of the protocol.

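### Withdrawal for surgery in the study region ends follow-up, so later safety, survival and 12-month data on both implants are no longer required

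*Combined protocol and SAP*

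**What the plan says.** Section 3.7.3 lists grounds on which the investigator may withdraw a patient. One is "Subject requires surgical treatment during the course of the study in the region of the mouth being evaluated in the study". The reason for the surgery is not restricted, so treatment of a problem at a study implant qualifies. A second, narrower ground is an "SAE or AE, which in the opinion of the Investigator prevents" further participation. Withdrawal is documented on a termination page with the reason. Section 3.7.3 adds: "Withdrawn patients will be replaced in case the recruitment is still ongoing".

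The stop rules are elsewhere. Under 7.3.12, adverse-event collection "ends after a patient withdraws from the study or completes the final study visit". Under 7.3.13, device-deficiency collection "ends after the last study required treatment", with no mention of withdrawal.

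Three assessments depend on the patient still being seen:

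- **Survival.** Section 7.3.8 says: "A surviving implant is defined as an implant in place at the time of the follow-up". It is therefore ascertained at visits.
- **PPD and BoP.** Table 2 schedules them at Visit 9 only. Section 3.4.2 explains their role: "these parameters are an indicator to determine the incidence of peri-implant diseases".
- **Periapical film.** Table 2 schedules films at Visits 2, 7 and 9. The flag for bone loss above 1.5 mm (footnote to Table 5) compares loading with Visit 9.

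Section 9.1 states that missing primary and secondary outcomes are not imputed. Section 9.2 analyses study-implant survival by Kaplan-Meier and assesses the safety co-primary descriptively.

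**The concern.** Surgery in the study region can be a consequence of how a study implant is doing. A rule that allows follow-up to end at that point allows data to go missing for a reason related to the outcome.

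Two analyses are exposed. Kaplan-Meier estimation assumes that implants censored at a given time have the same future risk as those still followed, and an implant just operated on may not. The safety co-primary rests on listings and tables of adverse device effects and of device deficiencies with serious potential, so it shows only what was collected.

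The paired design widens the loss, because withdrawing the patient also ends follow-up of the partner implant. The decision is discretionary. Section 7.2.2 blinds the patient and separates the assessor from the operator, but does not say that whoever decides on withdrawal is unaware of the surface.

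**Working it through.** The plan gives no figure of its own here. The 20% dropout allowance in 9.4 is not split by reason. The check therefore covers what remains required after withdrawal, and how much of the schedule that leaves out.

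**1. Status of each item after investigator withdrawal for surgery**

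| Item | Status | Source |
|---|---|---|
| Triggering event, if an AE | recorded | 7.3.12 |
| Withdrawal reason | recorded | 3.7.3 |
| AEs already open | pursued to resolution or last data queries | 8.4 |
| Safety set membership | kept | 9.3 |
| ITT membership | kept, given one follow-up measurement | 9.3 |
| New AEs and ADEs | collection ends | 7.3.12 |
| Later survival status, both implants | not required | 7.3.8, Table 2 |
| PPD/BoP | not required | Table 2 |
| Visit 9 film and bone-loss flag | not required | Table 2, Table 5 footnote |

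Section 8.4 has rules for screening failures and for patients lost to follow-up, but none specific to investigator-withdrawn patients.

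**2. Assessments lost for one withdrawn patient (Table 2)**

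- Survival is checked at Visits 3 to 9, which is 7 checks. Withdrawal just after Visit 7 loses Visits 8 and 9, or 2 of 7. Just after Visit 8 it loses 1 of 7.
- One periapical film follows loading (Visit 9). Withdrawal between loading and Visit 9 loses 1 of 1.
- PPD/BoP is read once (Visit 9). The same withdrawal loses 1 of 1.

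**3. Share of the AE-collection period lost, at nominal visit times**

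Collection starts at screening, which may be up to 10 weeks before placement. Loading is 10 weeks after placement, and Visits 8 and 9 are 6 and 12 months after loading. Ten weeks is 70/30.4 = 2.30 months.

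- Shortest period (screening adds almost nothing): 2.30 + 12 = 14.30 months.
- Longest period (full 10 weeks of screening): 2.30 + 2.30 + 12 = 16.60 months.
- Withdrawn just after Visit 7: 12/16.60 = 72% to 12/14.30 = 84%.
- Withdrawn just after Visit 8: 6/16.60 = 36% to 6/14.30 = 42%.

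**4. Where censoring can be informative**

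- Implant lost before or at withdrawal: counted as an event, so nothing is hidden.
- Implant operated on, still in place, patient withdrawn: with no later status required, both implants would ordinarily be censored then. For the operated implant, the reason may be linked to its later risk.
- Withdrawal unrelated to either implant: ordinary censoring.

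Only the second case is at issue. Section 9.2 refers to the SAP for detail. The text available for this review contains no separate censoring rules, so these could not be checked.

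**The case against.** The strongest case against is that the important events are already captured. Implant loss is a listed adverse event and a survival endpoint, the withdrawal reason is mandatory, open events are pursued, and the patient stays in the safety set. This stands. It narrows the gap to later new events, later status of both implants and the 12-month readings.

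Second, the adverse-event ground covers only events that prevent participation, and any sensible remedy must except patients who cannot attend. This also stands, so the point rests mainly on the surgery ground.

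Third, 3.7.3 and 11.3.1 advise withdrawn patients of the need for follow-up visits, including for safety data. But this is advice and requires no assessment. In 11.3.1 it concerns patients who want to withdraw. In 3.7.3 it follows text on the patient's own withdrawal, and its wider reach is unclear. Routine films may exist, since 7.3.1.2 describes them as standard practice, but nothing requires their upload or reading after withdrawal.

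Fourth, surgery may itself alter bone level, PPD and BoP, and 9.1 openly plans to stop considering a subject's data when a scenario affects one implant more than the other. That is a reason to handle the reading carefully in analysis. It is not a reason to leave it uncollected.

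A reader might infer more than the documents support:

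- **That failures disappear from the record.** They do not, as shown above.
- **That the rule favours SLActive.** A selection pattern that inflates the non-inferiority error can be constructed, but it must assume that the worst SLActive implants are the ones withdrawn. Nothing in the plan says so.
- **That an ITT bone-level comparison is biased.** Section 9.3 bases the primary effectiveness analysis on the PP set, and the available text specifies no ITT bone-level analysis.
- **That every missed bone-loss flag is a missed ADE.** A flag leads to discussion between the study manager and the principal investigator, not automatically to an ADE.

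**Conclusion.** The point holds for the surgery ground. The plan permits follow-up to end for a reason that can be related to implant outcome, and no provision requires the remaining safety, survival and Visit 9 data. This can make Kaplan-Meier censoring informative and reduces the evidence behind the safety co-primary.

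The size is known only per patient: after loading, the single post-loading film and the single PPD/BoP reading, up to 2 of 7 survival checks, and about 72% to 84% of AE collection if withdrawn just after Visit 7 (36% to 42% just after Visit 8). These shares assume nominal visit times and screening between 0 and 10 weeks before placement. The number of such withdrawals and the direction of any bias are unknown, so no bias figure is given.

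The primary analysis is not repaired by closing this gap. The PP set requires all follow-up visits and separately excludes any patient who loses a study implant. This is a worthwhile, inexpensive improvement, and it does not invalidate the design.

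**What to change.** Add to 3.7.3, in substance: *once both study implants are placed, surgery in the study region, or an adverse event that does not prevent attendance, does not end study follow-up unless the patient withdraws consent or cannot attend.*

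Then:

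- Continue AE, device-deficiency and implant-survival collection through Visit 9, with PPD/BoP and the periapical film for study implants still in place.
- Record the date and implant position of the surgery so that the analysis can account for it.
- Amend 7.3.12 to match, and give 7.3.13 the same end point.
- State in 9.1 that the rule to stop considering a subject's data does not apply to the safety and survival analyses.

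This concerns data collection only and changes no patient's treatment.

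The cost is modest. The visits are already scheduled, and 7.3.1.2 calls the films standard practice. Because the study began in October 2019, the change needs an amendment agreed by the sponsor and principal investigators, with ethics committee approval where 11.9 requires it. There is slightly more follow-up effort. A retained patient is not replaced, so one later excluded from the PP set uses one of the 60 − 51 = 9 places between planned enrolment and the 51 pairs in 9.4.
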